In contrast to the previous studies, Strijbos et al¹⁵ were successful in maintaining (and indeed improving) pulmonary rehab gains following 12 weeks of home-care rehabilitation. The investigators speculate that patients had become accustomed to exercise in their own domiciliary environment. This made it easier for them to continue exercising at home after the initial 12-weeks of training were over. A similar result was recently reported in the small proof-of-principle study of Ho et al.⁵⁸

The observations of Strijbos et al¹⁵ and Ho et al.⁵⁸ combined with our success in increasing exercise performance with RAS-enhanced music (see *preliminary results*, **Section B.6.1.**) lay the scientific foundation of the proposed experiments in our *Objective #3*. Specifically, these observations raise the possibility that combining RAS-music and home-based exercise training will result in greater long-term maintenance of rehabilitation gains than exercise-training alone.

A.3.4. Potential Confounders. Potential confounders to any pulmonary rehabilitation study include the patients' physiological and psychological phenotype and clinical factors.

A.3.4.1. Potential Confounders: Physiological Phenotype. Decreased exercise tolerance with attendant difficulty in achieving sufficient intensity of exercise during training hinders the effectiveness of rehab.⁶³ In addition to severity of lung disease, independent predictors of decrease exercise tolerance include quadriceps dimension, recruitment and strength, systemic inflammation (hsCRP and IL-6)⁶⁴ (see *work accomplished*).

A.3.4.2. Potential Confounders: Psychological Phenotype. Depression,^{49,60,65} anxiety^{49,60,65} and overall sense of fatigue^{62,66} can limit the effectiveness of pulmonary rehab as these factors may cause insufficient adherence to rehabilitation programs.

A.3.4.3 Potential Confounders: Clinical Factors. Approximately 15% of patients drop out from pulmonary rehab due to clinical factors such as COPD exacerbations,⁶⁷ cardiovascular disease (myocardial infarction, cerebrovascular accidents), or cancer.⁶⁸ Because of this, in the proposed investigation, we will assess the influence of the physiological and psychological phenotype and clinical factors on the effectiveness of RAS- enhanced and non RAS-enhanced home-based

rehabilitation (*Objective #4*).

A.4. Significance and Relevance to the VA.

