The resulting effect of this integrated synergy will be to promote greater functional gains (primary hypothesis) at the end of 12 weeks of home- based exercise training and to promote better maintenance of the benefits of pulmonary rehab at 24 weeks than in the no-music group (secondary hypothesis).

C.1.2. General Overview of Design. The proposed study has been designed as a randomized, controlled clinical trial in which COPD patients will be randomized into an exercise program with RAS-enhanced music (RAS- music group) or in an exercise program without music (no-music group). COVID 19 patients will be randomized into an exercise program with RAST-enhanced music (RAST- music group and strength training) or in an exercise program without music (no-music but will have strength training group). Patients will complete testing procedures at pre-randomization, at 6 weeks, immediately post-rehabilitation, and 24 weeks after enrollment. Testing at 6 weeks is included to provide interim follow-up should patients not complete the 12 weeks of training.

C.1.3. Sample Size Calculation.

Sample size was estimated based on a 2-group mixed model design with baseline, 6 and 12-week measurements. Our primary goal is to compare the difference in distance walked during the standard 6MWT over 12 weeks between groups (see **C.1.9.1.a.**). We estimate that the COPD target sample size of 68 patients per group completing 12 weeks will ensure 80% power to detect the differences between treatment arms using a two-sided significance level of 0.05, assuming a correlation of 0.70 between measurements. These estimates are based on our PAD pilot data and include similar standard deviations at baseline and at 6 weeks between groups and over time (232 feet), correlations between measurement of 0.76 to 0.86, and an increase of 87.2 feet at 6 weeks for the RAS- music group, with a slightly higher level for those completing the 12-week assessment. Based on the work of

Table. 2 COPD Study inclusion and exclusion criteria

Inclusion Criteria	Exclusion Criteria
• ≥ 40 yr. of age	• Respiratory infection/COPD exacerbation within the previous four weeks
• FEV ₁ ≤ 70%	• Exercise-limiting heart disease (Congestive heart failure – i.e., New York Heart Association Class III or IV; positive stress test or other indicators of heart disease or complaints of angina during the stress test)
• FEV ₁ /FVC <70%	• Exercise-limiting peripheral arterial disease (stops walking due to intermittent claudication)

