C.1.8. Time Summary. The two groups of patients will complete the same testing procedures at the same time intervals. In Tab. 5, we summarize the timeline for completion of the proposed research project.

C.1.9. Measures:

Table. 5 COPD Timeline for research completion															
	Year 1				Year 2				Year 3				Year 4		
Finalize data collection instruments/ Purchase supplies	x														
Screen and enroll patients	x	x	x	x	x	x	x	x	x	x	x	x	x	x	
Train and follow patients		x	x	x	x	x	x	x	x	x	x	x	x	x	x
Data entry/Coding/Cleaning	x	x	x	x	x	x	x	x	x	x	x	x	x	x	x
Quality monitoring				x				x				x			
Data analysis/Preparation reports								x				x		x	x
Presentations/Publications (presentations at AACVPR, ACSM, ATS, Chest)								x			x		x	x	x

Definition of abbreviations: AACVPR = American Association of Cardiovascular & Pulmonary Rehabilitation; ACSM = American College of Sports Medicine; ATS = American Thoracic Society

COVID 19 timeline

Table 3. Timeline for research completion															
	Year 1				Year 2				Year 3				Year 4		
Finalize data collection instruments/ Purchase supplies	x														
Screen and enroll patients	x	x	x	x	x	x	x	x							
Train and follow patients	x	x	x	x	x	x	x	x							
Data entry/Coding/Cleaning	x	x	x	x	x	x	x	x							
Quality monitoring				x				x				x			
Data analysis/Preparation reports								x				x			
Presentations/Publications (presentations at AACVPR, ACSM, ATS, Chest)								x			x		x	x	x

Definition of abbreviations: AACVPR = American Association of Cardiovascular & Pulmonary Rehabilitation; ACSM = American College of Sports Medicine; ATS = American Thoracic Society

C.1.9.1. Six-minute Walk Tests (6MWT): Patients will perform two 6MWT as fast as they can without running according to ATS recommendations (standard 6MWT)⁹⁷ and two modified 6MWT at their usual/leisurely walk pace (*leisurely-paced 6MWT*). Walking cadence during these tests will be used to adjust the RAS exercise prescription (RAS-music group). In addition, data from the *standard 6MWTs* will be used to test the primary hypothesis that exercise training with RAS-music elicits greater increases in *standard 6MWT* distance than exercise training alone. Please note that the *leisurely-paced 6MWT* are only completed at baseline. The *standard 6MWT* are repeated at all testing time points (baseline, 6 weeks, 12 weeks and 24 weeks).

C.1.9.1.a. Standard 6MWT: Patients will be instructed to walk back-and-forth a 100-foot long circuit as

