H1A: IN PATIENTS WITH COPD, IMPROVEMENTS IN 6-MINUTE WALKING DISTANCE WILL BE GREATER AFTER COMPLETING 12 WEEKS OF A HOME-BASED, EXERCISE PROGRAM WITH RAS-ENHANCED MUSIC THAN AFTER A HOME-BASED, EXERCISE PROGRAM WITHOUT MUSIC.

The analysis of the primary outcome (improvements in 6-minute walking distance) is based on all data collected during the intervention period—baseline, 6 and 12-weeks. We will use a mixed-model analysis that includes treatment, time and treatment-by-time interaction terms. Specifically, we will test whether the treatment- by-time interaction differs from 0. This model will automatically account for missing data

where missing at random is assumed. We will conduct a sensitivity analysis^{129,130} based on the results of the mixed model analysis to determine whether other assumptions regarding the missing data may produce different results. One component of the sensitivity analysis will also include adjustment for

baseline demographic and health covariates.

C.2.2. Statistical Analysis: Secondary Hypotheses

Statistical analysis for H_{1c} will parallel that of H_{1a} .

H_{1D} : THE RAS-ENHANCED MUSIC GROUP WILL DEMONSTRATE GREATER INCREASES IN HEALTH-RELATED QUALITY OF LIFE (QOL) THAN THE CONTROL GROUP.

Statistical analysis for H_{1d} will parallel that of H_{1a} .

H_2 : THE RAS-ENHANCED MUSIC GROUP WILL ACCUMULATE A GREATER VOLUME OF DAILY PHYSICAL ACTIVITY THAN THE CONTROL GROUP. THIS WILL BE DEMONSTRATED BY GREATER PHYSICAL ACTIVITY AT 12 WEEKS (ACTIGRAPHY).

Statistical analysis for H_2 will parallel that of H_{1a} .

H_3 : THE RAS-ENHANCED MUSIC GROUP WILL MAINTAIN IMPROVEMENTS IN MEASURED AND PERCEIVED FUNCTION AT 24 WEEKS TO A GREATER EXTENT THAN THE NO-MUSIC CONTROL GROUP.

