In the statistical analysis of H_3 , we will use independent t-tests to compare the changes in measured function (distance walked in the 6MWT and perceived function (questionnaires) between 12 and 24-weeks between the RAS-music and the no-music groups. We will also conduct paired t-tests within each group to determine whether values at 24 weeks are worse than those at 12 weeks. These computations will be based on those patients with 12 and 24-week data. To assess whether patients included in the H_3 analysis are representative of the original randomized groups, we will also compare demographic and health measures (i.e., FEV₁ percent predicted, comorbidities, depressive symptoms and exacerbations) of patients included in the H_3 analysis to patients who were not.

C.2.3. Statistical Analysis: Exploratory objective: [exploratory objective not reported]

TO ASSESS IMPACT OF PHYSIOLOGICAL AND PSYCHOLOGICAL PHENOTYPE AND CLINICAL FACTORS ON RESPONSIVENESS TO REHABILITATION ACHIEVED WITH AND WITHOUT CONCURRENT USE OF RAS-MUSIC. PHYSIOLOGICAL FACTORS INCLUDE: SYSTEMIC INFLAMMATION (HS-CRP), QUADRICEPS STRENGTH, RECRUITMENT AND FATIGUE, QUADRICEPS FUNCTION AND DIMENSION AFTER REHABILITATION. PSYCHOLOGICAL FACTORS INCLUDE: SELF-EFFICACY, ANXIETY AND DEPRESSION. CLINICAL FACTORS INCLUDE: ADHERENCE TO THE 12-WEEK PROGRAM, ADHERENCE TO FOLLOW-UP AND NUMBER AND SEVERITY OF EXACERBATIONS.

To assess the impact of the above confounders two separate analyses will be conducted: (a) A linear regression model with changes from baseline to 12 weeks of training as the dependent variable, and assigned treatment group, physiologic and psychologic phenotype and clinical factors as the independent variables, and

(b) A mixed model ANOVA with baseline, and 12 and 24 weeks measurements as dependent measures and assigned group, physiologic and psychologic phenotype and clinical factors as the independent variables.

C.3. Expected Outcome: We expect to demonstrate that improvements in 6-minute walking distance from baseline to 12 weeks will be greater after completing 12 weeks of a home-based, exercise program with RAS- music than after a home-based, exercise program without music.

C.4. Alternative Outcomes. Our primary hypothesis will be rejected if, at 12 weeks, improvements in 6-minute walking distance are not greater with exercise-training plus RAS-music than with exercise-training without music. In this case, at least three alternative outcomes will be considered.

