Three, limited adherence to home-based exercise: please see point One, *section C.4.2.*

C.4.4. Miscellaneous limitations and alternative methods

C.4.4.1. Medications: Medications may be adjusted throughout the study; such adjustments may affect outcome variables including exercise endurance. *Proposed Action:* Patients must be on stable therapy before enrollment. From our previous experience, we expect that several patients will require minor adjustments of their anti-hypertensive medication throughout the study. Medication lists and doses will be documented at each evaluation period. If patients require significant medication changes as judged by Drs. [name] (Pulmonary) or [name] (Data Safety Monitoring), appropriate statistical adjustments will be made.

C.4.4.2. Patients withdrawal: Patients may withdraw from the study at a higher rate than anticipated. *Proposed Action:* Since we use intent-to-treat analysis, any patient completing at least six weeks of training will be included in the analysis. If more than 20% of patients withdraw - or have to be withdrawn - prior to the sixth week of training, we will increase the number of randomized patients accordingly.

C.4.4.3. Lack of internet access: Some patients have no internet access. (Patients need internet access to sync the Fitbit). *Proposed Action:* Patients without internet access will be provided with a list neighborhood locations with Wi-Fi hotspots. Alternatively, patients will be free to come to the lab to sync

the Fitbit.

C.4.4.4. Music in the control group: Some patients in the control group may be used to listening to music while walking. *Proposed Action: Through the study, patients in the no-music group will be instructed to avoid listening to any music while walking.* In addition, at the end of the study, we will ask patients in the control group whether they listened to music while walking. Appropriate statistical adjustments will be made if needed.

C.5. Potential Problems.

C5.1. Insufficient patient enrollment. This is a very unlikely considering the large number of patients with COPD cared for at Hines VAH and our excellent track record.^{3,4,80,94} In addition, we could enroll patients from the Jesse Brown VA located 10 miles east of Hines. We could advertise in local newspapers and on Chicago Transit Authority busses.⁹⁶

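### Both exploratory Objective 4 models omit the week-6 walk, so patients who leave between weeks 6 and 12 give no follow-up outcome and factor effects may be biased in either direction

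*Combined protocol and SAP*

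**What the plan says.** - **Motivation (A.3.4.3).** The plan states: "Approximately 15% of patients drop out from pulmonary rehab due to clinical factors such as COPD exacerbations". After this drop-out remark it continues: "Because of this, in the proposed investigation, we will assess the influence of the physiological and psychological phenotype and clinical factors". The sentence goes on to name the effectiveness of the two home programmes as the thing influenced. A.1 and C.2.3 describe the same objective as responsiveness to rehabilitation and label it exploratory.
- **Purpose of week 6 (C.1.2).** "Testing at 6 weeks is included to provide interim follow-up should patients not complete the 12 weeks of training".
- **Visits (C.1.9.1).** The standard six-minute walks "are repeated at all testing time points (baseline, 6 weeks, 12 weeks and 24 weeks".
- **Primary analysis (C.2.1).** H1a "is based on all data collected during the intervention period—baseline, 6 and 12-weeks", fitted as a mixed model assuming data missing at random.
- **Early leavers (C.4.4.2).** "any patient completing at least six weeks of training will be included in the analysis".
- **Objective 4 models (C.2.3).** Model (a) is "A linear regression model with changes from baseline to 12 weeks of training as the dependent variable". Model (b) is "A mixed model ANOVA with baseline, and 12 and 24 weeks measurements as dependent measures". The explanatory variables in both are assigned group and the physiological, psychological and clinical factors, including adherence and exacerbations.

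**The concern.** The factors studied in Objective 4 are ones that the plan links to leaving the programme. The patients most likely to lack a week-12 walk may therefore be those in whom the factors acted most strongly. The week-6 visit exists for such patients, yet neither model lets their week-6 result count.

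What is at stake is interpretation. Sections C.4.1 to C.4.3 turn to the exploratory objective for reasons why the trial might be null or unfavourable, and use those reasons to shape later studies. A distorted coefficient for exacerbations, for example, could point that planning the wrong way.

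**Working it through.** **1. Visits set against models**

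| | Baseline | Week 6 | Week 12 | Week 24 |
|---|---|---|---|---|
| Walk measured | yes | yes | yes | yes |
| H1a (C.2.1) | used | used | used | no |
| C.2.3 (a) | used | no | used | no |
| C.2.3 (b) | used | no | used | used |
| Patient leaving for good between weeks 6 and 12 | has | has | lacks | lacks |

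Such a patient gives H1a a follow-up value, is excluded from (a), and gives (b) a baseline value only. If (b) is run on complete records, the patient gives it nothing.

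**2. The plan's own figures (C.1.3)**

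- SD of change = 232 × √(2 × (1 − 0.70)) = 179.7 ft.
- For a difference of 87.2 ft at two-sided 0.05 and 80% power, n per group = 2 × (1.960 + 0.842)² × 179.7² / 87.2² = 66.7, so 67. The plan says 68, at which power is 80.8%.
- 136 / 0.80 = 170 randomised, and 170 / 0.70 = 242.9, so 243 enrolled.

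These reproduce. The plan gives no power or sample size for Objective 4.

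**3. How many patients**

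Planned attrition by week 12 is 8%: 170 × 0.08 = 13.6, about 14. At the 15% background rate in A.3.4.3 it would be 170 × 0.15 = 25.5, about 26. Both are upper limits, because the plan does not split losses before and after week 6, and week 6 cannot help those who leave before it.

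**4. Direction and size of bias**

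A large simulation (2,000,000 patients) isolates bias from sampling error.

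- From the plan: SD 232 ft, correlation 0.70, a week-12 music gain set at 87.2 ft, and 25% exacerbating (the 24-week figure in C.1.10).
- Assumed: exacerbation effect −87.2 ft at week 12 and 70% of that at week 6; a 60 ft music gain at week 6; logistic drop-out after week 6 with log-odds +1.5 for an exacerbation. Response terms are per 180 ft of change: 0.8 in rows B, C and E, and 1.5 among exacerbators only in row D.

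Entries are the estimated week-12 exacerbation coefficient as a percentage of the true value, at 8% / 15% loss. The second column stands in for (b) with a likelihood fit to baseline and week 12.

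| Drop-out depends on | Model (a) | (b)-type, no week 6 | Likelihood with week 6 |
|---|---|---|---|
| A. Exacerbation only | 100 / 99 | 100 / 99 | 100 / 99 |
| B. Exacerbation and poor week-6 change | 89 / 83 | 92 / 88 | 100 / 100 |
| C. Exacerbation and poor, unseen week-12 change | 77 / 63 | 80 / 68 | 83 / 74 |
| D. Exacerbation, with poor week-6 change acting only in exacerbators | 73 / 59 | 81 / 71 | 100 / 100 |
| E. Exacerbation and good week-6 change | 107 / 111 | 105 / 108 | 100 / 99 |

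**5. A second set of assumptions**

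Here 13.4% exacerbate by week 12 (1 − √0.75, a constant rate over 24 weeks), with assumed effects of −70 ft at week 6 and −100 ft at week 12. At 8% / 15% loss, model (a) gives:

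- −100 / −100 ft if drop-out depends on exacerbation only;
- from −97 / −94 to −79 / −69 ft as the assumed dependence on poor response strengthens;
- −107 / −110 ft if good responders leave.

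With week 6 included, the estimate is about −100 ft in each case. At 8% loss the shift towards zero is therefore 3 to 21 ft in 100.

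**6. Against sampling error**

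With 170 − 14 = 156 patients and 13.4% exacerbating, the standard error is about 179.7 / √(156 × 0.134 × 0.866) = 42 ft. A shift of 3 to 21 ft is at most about half a standard error.

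**The case against.** The case for leaving C.2.3 alone has real force.

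- **It is exploratory.** No power is claimed, the C.2.3 heading carries a note that the exploratory objective is not reported, and C.4 uses the results mainly to plan later work. This stands and keeps the severity low.
- **The primary analysis already honours week 6.** H1a uses it, and neither C.1.2 nor C.4.4.2 names Objective 4. A reader might infer that C.4.4.2 is breached, but its reference to the analysis can fairly be read as the primary one. What remains is available data left unused.
- **Exacerbations near a visit defer testing (C.1.10).** This limits missed walks among patients who stay. It does not help those who leave.
- **Week 6 is not a complete cure.** In row C it recovers only part of the loss. Quadriceps twitch is measured at week 12 only (C.1.6.1.c), and adherence to the 12-week programme is cut short in leavers.

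Two stronger readings are tempting. The first is that the effects of exacerbations and adherence are definitely understated. The documents give no drop-out mechanism: A.3.4.3 blames clinical events and says nothing about a poor week-6 walk. Rows A and E show no bias and overstatement, and adherence was not simulated. The second is that Objective 4 is meant to explain drop-out. Drop-out motivates it, but its outcome is response to rehabilitation, and the 15% is a background rate, not this trial's planning figure.

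**Conclusion.** The structural point is certain: neither Objective 4 model uses a week-6 outcome that the trial collects and already analyses elsewhere. The consequence is conditional. Coefficients move towards zero if poor responders leave, away from zero if good responders leave, and are unaffected if leaving depends only on factors in the model.

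At 8% loss, and with drop-out driven by observed week-6 response, the attenuation in model (a) is roughly 3% to 20%. It reaches 27% in the strongest case tried. These sizes rest on assumed exacerbation effects and drop-out models, and they treat all of the 8% as leaving after week 6. At the planned attrition at most about 14 of 170 patients are involved, and the shift is modest beside the coefficient's standard error. In none of the cases tried did adding week 6 make the bias worse. This is a cheap improvement of low severity to an exploratory analysis.

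**What to change.** In C.2.3:

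1. Replace model (a) with the C.2.1 likelihood mixed model on baseline, 6 and 12 weeks, adding factor-by-time terms and reading the week-12 contrast.
2. Add week 6 to model (b), giving baseline, 6, 12 and 24 weeks, and state that it is fitted by likelihood so that partial records are kept.
3. Fit factors measured only at week 12, such as quadriceps twitch, in a separate model labelled as completers only. In the main model they would remove the early leavers again.
4. Say how adherence and exacerbation counts are defined for a patient who leaves early.

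The cost is SAP wording and a little programming, with no new data. The estimates would rest on the missing-at-random assumption that the primary analysis already makes, and bias would be only partly removed if drop-out depends on unseen week-12 status.

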• Mean SpO ₂ ≥ 88% at peak exercise (with or without oxygen supplementation)	• Stops exercise for arthritic pain in knee or hips
• Ability to hear music	• Inability to walk on the treadmill
	• Any unforeseen illness or disability that would preclude exercise testing or training
	• Participation in a formal exercise program within the previous 12-weeks

Liu et al.,¹¹ we estimate no change in the 6MWT in the no-music exercise training group.

COVID 19 sample size was estimated based on a 2-group design with pre- and post-test measurements. Our primary goal is to compare the difference in distance walked during the *standard 6MWT* at 12 weeks between groups. We estimate that over a two-year period we will ensure complete data collection on a total of 72 patients (36 per group). This will ensure a 58% power to detect the differences between treatment arms using a two-sided significance level of 0.05, assuming a correlation of 0.65 between measurements. Our pilot data used to support this estimate include the most conservative correlation observed between measurements ($r=0.65$), and an increase of 41 meters at 12 weeks for the intervention group.

According to the local IRB, enrollment is the equivalent to a patient signing an informed consent. In our three latest studies,^{3,4,94} 30% of patients who signed the informed consent (i.e., enrollees) did not meet pulmonary function criteria or did not qualify for other reasons.⁹⁵ Moreover, based on our previous work, we expect an attrition 12 weeks after randomization of about 8%, and an attrition 24 weeks after randomization of 20%. Accordingly, to have complete data in 136 COPD patients as required by our power calculation (see above), we plan to 'enroll' 243 COPD patients (i.e., signed informed consent) expecting to 'randomize' 170 of them, and to lose 34 of this latter group by week 24 (end of the study). We will enroll 100 patients with COVID 19 into this study.

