After baseline testing is completed (Tab. 4) and study criteria are met, COPD patients will be randomized to exercise training with RAS-enhanced music (RAS-music group) or exercise training without music. COVID 19 patients will be randomized to exercise training with RAST-enhanced music and strength training (RAST-music group) or exercise training without music and with strength training. We chose a no-music control group as opposed to music without RAS-enhancement not to contaminate the control group. Music

can have strong bass or, when listening to music, individuals can augment the bass. Strong bass could provide an unintended RAS-like intervention. Testing and measures are described in sections **C.1.9.1 t**

COVID 19 Inclusion/Exclusion Criteria

Inclusion Criteria

- ≥ 18 yrs. of age
- Previous hospital and/or emergency room visit for laboratory-confirmed COVID-19 diagnosis.
- Able to walk independently
- Mean SpO₂ ≥ 88% at peak exercise (w/ or w/o O₂)
- Ability to hear music

Exclusion Criteria

- Able to walk more than 550 meters during a standard 6-minute walk test
- Exercise limiting heart disease (complaints of angina during the 6- minute walk distance tests or other indicators of exercise-limiting heart disease)
- Congestive heart failure (New York Heart Association Class III or IV)
- Exercise-limiting peripheral arterial disease (stops exercise due to intermittent claudication)
- Stops exercise due to arthritic pain in the knee or hips (self-report)
- Pregnancy

C1.9.5.

Randomization will be computer-generated with permuted blocks with random block sizes. This strategy is intended to preserve balance in the randomization of patients as to maintain unpredictability of the treatment assignments. Group assignment will be managed by the Hines Cooperative Studies Program Coordinating Center (CSPCC). When a patient is ready for randomization, we will contact the CSPCC to receive the randomization designation. To maintain testing integrity, [name], [name] or their designee will supervise patient testing and will be blinded to group assignment. When data are reviewed, the data will be void of any identifiers. [name] (PI, pulmonologist) will remain blinded to group assignment. If patients develop medical problems during the study [name] can request to be unblinded. When unblinded, the two physicians will not supervise further exercise testing for those given

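### Does the COVID sample size fail to follow from 100 consented patients, so that power is 53% rather than 58%?

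*Combined protocol and SAP*

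**What the plan says.** Section C.1.3 (Sample Size Calculation) treats the two cohorts in turn.

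- **COVID target.** "We estimate that over a two-year period we will ensure complete data collection on a total of 72 patients (36 per group"). The next sentence reads "This will ensure a 58% power to detect the differences between treatment arms", at two-sided 0.05 with a correlation of 0.65 between measurements. The pilot effect is a 41 m gain at 12 weeks in the intervention group. No SD and no control-group change are given for COVID.
- **COVID enrolment.** "We will enroll 100 patients with COVID 19 into this study". The section records that, for the local IRB, "enrollment is the equivalent to a patient signing an informed consent".
- **Screen failure.** In the team's three latest studies, "30% of patients who signed the informed consent (i.e., enrollees) did not meet pulmonary function criteria or did not qualify for other reasons".
- **Attrition.** From previous work, "we expect an attrition 12 weeks after randomization of about 8%, and an attrition 24 weeks after randomization of 20"%.
- **COPD chain.** To have complete data in 136 COPD patients, the sponsor plans 243 consented, "expecting to 'randomize' 170 of them, and to lose 34 of this latter group by week 24".

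There is no corresponding COVID chain: no COVID screen-failure rate, attrition rate or number to be randomised, and no statement of the visit at which data must be complete.

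**The concern.** The COPD paragraph shows each step from consent to complete data. The COVID sentence that closes it gives only the starting number, and the end point stands in the paragraph before. A reader naturally carries the section's rates across, and 30% screen failure alone leaves 70 of 100, already below 72 before anyone drops out.

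Some COVID patients can also fail after consent, because certain COVID criteria are tested on study. One exclusion is "Able to walk more than 550 meters during a standard 6-minute walk test"; others concern oxygen saturation at peak exercise and angina during the walk. Section C.1.4 adds that about 8 patients a month will be enrolled and 5 to 6 of them randomised, a failure rate of 25% to 37.5%.

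The 6-minute walk distance is the COVID primary hypothesis. If 72 were out of reach, the stated power, already only 58%, would be too favourable, and that would matter when reading a null result.

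**Working it through.** **1. Reproduce the COPD chain.** 243 × (1 − 0.30) = 170.1, so 170 randomised. 170 × (1 − 0.20) = 136, with 34 lost. This matches the plan and shows that it used 30% and the 24-week attrition of 20%.

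**2. Try to reproduce the 58%.** No COVID SD is stated, so this cannot be done from the COVID inputs. The only SD in C.1.3 is 232 feet, from the peripheral artery disease pilot: 232 × 0.3048 = 70.7 m. With a 41 m difference (no change in controls assumed), 36 per group and a two-sided two-sample t-test:

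| Analysis scale | SD (m) | Power |
|---|---|---|
| 12-week value only | 70.7 | 68% |
| Change score, 70.7 × √(2 × (1 − 0.65)) | 59.2 | 83% |
| Baseline-adjusted, 70.7 × √(1 − 0.65²) | 53.7 | 89% |

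None gives 58%, so the sponsor used some other SD or control change. Solving backwards, 58% at 36 per group corresponds to a standardised difference of 0.517, or 41 / 0.517 ≈ 79 m on the analysed scale. Power at any other number below is a rescaling from that value.

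**3. Apply the section's rates to 100 COVID consents.**

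- Randomised: 100 × 0.70 = 70.
- With 12-week data: 70 × 0.92 = 64.4, about 64 (32 per group). Power is 53.0%, or 52.5% to 53.5% if 58% was rounded from 57.5% to 58.5%.
- With 24-week data: 70 × 0.80 = 56 (28 per group), power about 48%.
- No attrition: 70 (35 per group), power about 57%.

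**4. What 72 of 100 requires.** Total loss is 1 − 72/100 = 28%. With 8% attrition, 72 / 0.92 = 78.3 must be randomised, so screen failure may reach 21.7%. With 20% attrition, 72 / 0.80 = 90 must be randomised, so it may reach 10%.

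**5. Sensitivity to COVID screen failure, at 8% attrition.**

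| Screen failure (assumed) | With 12-week data | Power |
|---|---|---|
| 10% | 83 | 64% |
| 20% | 74 | 59% |
| 21.7% | 72 | 58% |
| 25% | 69 | 56% |
| 30% | 64 | 53% |

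Attrition alone would leave 92 or 80 of 100, above 72. Any shortfall therefore turns on screen failure.

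**6. Does the 30% belong to COVID?** C.1.3 ties it to earlier studies, names pulmonary function criteria among the reasons, and applies it only in the sentence about 136 COPD patients. Set beside COPD Table 2, the COVID list has no FEV₁ or FEV₁/FVC threshold. It also has no positive-stress-test criterion, no treadmill requirement, no recent-exacerbation or recent-exercise-programme exclusion, and no catch-all for unforeseen illness. It adds the 550 m ceiling and pregnancy. The net direction cannot be worked out from the documents. The 5 to 6 of 8 in C.1.4 does not settle it either: the enrolment row of Table 3, to which it refers, sums to 50 + 80 + 80 + 33 = 243, the COPD figure.

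**The case for a change.** The strongest case for a change is that the sponsor wrote out the chain for COPD, evidently thinking it worth showing, and left it out for COVID while saying that 72 and 58% will be ensured. The 30% also covers patients who failed for reasons other than lung function, and COVID patients face tested criteria of their own. If the sponsor had a lower COVID rate in mind, stating it would cost a sentence. The rule in C.4.4.2 that patients completing six weeks are analysed does not rescue 72, since at 30% failure no more than 70 are randomised.

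Much of this stands. Neither 72 nor 58% can be derived from the text, and the missing SD and control change are a more basic gap than the missing chain. But it does not show that 72 is wrong. The sentence containing the promise opens as an estimate. A failure rate modestly below 30% meets the target, and a lower one exceeds it. C.4.4.2 also provides for randomising more patients if over 20% withdraw before week six, which covers early attrition though not screen failure. Printing 64 and 53% in the plan would put a COPD-applied rate where no COVID rate exists, and would rescale a 58% that cannot itself be checked.

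**Conclusion.** No change follows. The omission is real, but it is planning detail and not an arithmetic error. The stated 28% total loss is compatible with everything in the documents, provided COVID screen failure is at most about 22% with 8% attrition, or 10% if complete data means week 24 with 20% attrition.

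The figure of about 64 patients and 53% power is one row of a range running from 83 patients and 64% (10% failure) to 64 and 53% (30% failure). It rests on two assumptions the documents do not establish: that the 30% carries over to COVID, and that 58% is right at 36 per group. Even if both hold, the difference is about 5 percentage points in a comparison the plan already declares to have low power.

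Writing out the chain would not alter the enrolment of 100, the randomisation or the analysis. The precision actually achieved will be visible from the number analysed and the confidence interval, whatever power was projected. A sponsor revising C.1.3 for other reasons could add the COVID rates, visit, SD and control change, but the trial's conclusions do not depend on it.
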